There is no standard of care for rehabilitation following THA.⁵³ Observed practice patterns from previous investigations³³ and discussion with physical therapists indicate that patients receive rehabilitation services during the 2-3 day hospital stay after THA, but not routinely after hospital discharge. Yet, to control for attention and volume of rehabilitation for the FSI group, patients in the control group will attend outpatient physical therapy for 14 visits (40 minute sessions) over 8 weeks. This control program will mimic the typical postoperative experience for patients in our community, in which patients independently manage their activity. This program will focus on patient education, functional ADL training, and therapeutic exercise. However, the activities in the exercise domain will be limited to low load exercise such as isometric muscle exercise, ROM, and flexibility activities. These activities are specifically designed to mirror usual care activity. These activities will not include progressive strength training exercise or specific functional activity to improve pelvic stability and core muscle strength, which are exclusive to the FSI group.

A1.3. Data Collection and Outcome Measures

Baseline testing will occur 2 weeks prior to THA. To develop a more precise estimate of the trajectory of recovery after THA, we will assess outcomes at 3 times postoperatively. Postoperative testing will occur at intervention mid-point, 4 weeks (POST1); intervention end-point, 8 weeks (POST2) (primary endpoint); and late recovery, 26 weeks (POST3). The 4-week test will allow for identifying if any changes occur early in the intervention, the 8-week test will serve as the primary endpoint for assessing intervention efficacy, and the 26-week test is important to assess persistence of intervention effects. Testing will be performed using standardized procedures described below. Testing may occur remotely via Zoom or video call, at the participant's home, or on the Anschutz campus.

Phase	Functional Strength Integration Program (FSI) *	Control Group Program (CON)**

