
A1.5. Data Management

Study data will be collected and managed using the REDCap (Research Electronic Data Capture) platform. REDCap is a secure, web-based application designed to support electronic data capture for research studies, providing user-friendly case report forms, real-time data entry validation (e.g. for data types and range checks), audit trails, transaction logs, and a de-identified data export mechanism to common statistical packages. Data will be placed on the REDCap Instance at the Colorado Clinical and Translational Sciences Institute (CCTSI). This data will be used solely for the purposes defined for this specific study. Data placed on the CCTSI REDCap Instance will not be accessed or used for any other study or purpose, and will only be accessed by VA-credentialed personnel. The CCTSI REDCap Instance is a highly secure, nationally-utilized data management system, and it is housed within the highly-secure environment at the University of Colorado.

A1.6. Data Analysis

The primary outcome for this study is change in 6MW distance from baseline to POST2 (end of study intervention). Secondary physical function and muscle performance outcome measures include change in 4MW, 30 sec sit-to-stand, isometric hip abductor strength, and hip abductor muscle endurance. Secondary self-report outcome measures include the WOMAC and VR-12. Measures of movement compensation after unilateral THA include *peak internal hip abduction moments* during **walking from baseline to POST2**. Preliminary descriptive and graphical analyses (e.g. boxplots, scatterplots, and profile plots over time) will be used for data checking and visualization. All analyses will assume a two-sided test of hypothesis, with a significance level of 0.05, and be performed in SAS v9.4 or higher and R v3.2.2 or higher.

Primary Analysis: The primary analysis will be an intent-to-treat comparison between groups of the change in 6MW distance from baseline to POST2 (end of intervention). Statistical inference regarding the difference between treatment groups will be based on the estimated coefficient for a group indicator variable in an analysis of covariance (ANCOVA) model with the change from baseline at POST2 for the 6MW distance being the response variable. Additional covariates will include the stratification variables (surgical approach and Veteran/non Veteran) and the baseline value of the 6MW distance to improve the precision of the estimate.

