The conclusion about differences between treatment groups will be determined by this single statistical test to protect against an elevated risk of false positive conclusions. A similar analysis will be performed on the change from baseline to POST3 to determine persistence of group differences to 26 weeks. Additionally, a sensitivity analysis will be performed utilizing a mixed-effects model and all available data, with estimation of the change from baseline to POST2 and POST3. If the sensitivity analysis is not consistent with the primary analysis, the results will be considered inconclusive.

Secondary Analyses: Differences between groups in the secondary outcomes for physical function, muscle strength and endurance, and peak internal hip abduction moment, from baseline to POST2 will also be analyzed as described above. All outcomes will be analyzed at POST3 to evaluate the long-term impact and sustainability of the FSI training. We anticipate that secondary outcomes will be correlated with the primary outcome, so that similar effects on secondary outcomes will reinforce significant differences in the primary outcome. Failure to observe consistency between primary and secondary outcomes will be taken as evidence that the effects of FSI intervention are not clear, and that further study is necessary to resolve inconsistencies. This approach reduces the risk of false-positive conclusions resulting from multiple statistical tests.

A1.7. Sample Size Estimates

Statistical power was estimated using variability estimates from Heiberg *et al.* (2015), where the change in 6MW distance was assessed for 60 participants following THA.⁹⁸ Because Heiberg's target population was comparable to that currently proposed, and their sample size was 3 times that of our pilot study, our estimates using these data⁹⁸ are expected to serve as the best estimate of samples size. As such, the observed SD at 3 months post-surgery for the sample was 81.3. Based on this SD, a 2-sample, 2-sided t-test at the 5% level with 80 patients (40 per group) would have 90% power to detect a clinically meaningful difference of at least 59.7 meters.⁹⁹ The primary analysis using linear regression will be conditioned on the baseline value of each outcome measure, in addition to the sex and surgical approach stratification variables, thus improving the precision of (and giving greater power to) the estimates. We will recruit 150 participants (75/group) to allow for loss to follow-up.

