A1.8. Alternative Approaches and Limitations

Missing Data. All participants with outcome measurements will be included in the intent-to-treat analysis. Although we will encourage participants to be fully compliant to their assigned treatment regimen and testing sessions, they will not be dropped from follow-up measurements for lack of compliance. The importance of complete follow-up will be stressed during enrollment and consent, and repeated during study participation. Participants will be contacted repeatedly if they miss follow-up visits, and all efforts will be made to get participants to return for scheduled follow-up visits. Although statistical methods can be used to "adjust" for missing data, these methods rely on the untestable assumption that data are "missing at random" so that the effect of the missingness can be removed through statistical modeling. We will instead focus on preventing missed follow-up visits.

Differences in surgical approach. There remains a paucity of prospective data comparing physical function outcomes with posterolateral versus direct anterior THA surgical approaches. Therefore, including both surgical approaches (and stratifying by approach) will increase the generalizability of the study. Furthermore, this strategy may also provide additional insights regarding any potential differences in surgical approaches. Finally, we have intentionally chosen not to include less common, alternative THA surgical approaches (e.g. direct lateral) to focus stratification on the most commonly used THA surgical approaches.

A1.9. Timeline

Anticipated project timeline and cumulative enrollment. Local IRB approvals will be finalized prior to initiating the investigation. Study enrollment will start in months 3-4 and continue through the first part of year 4, with a targeted accrual rate of 2-3 patients/month. Abstract and manuscript preparation will begin in years 2-3, but will increase in year 4.

A1.10. Future Investigation

1) Evaluate strategies for dissemination and implementation of study findings in clinical practice.

While the proposed FSI intervention is novel, it has been designed for practical implementation in clinical settings to facilitate more rapid dissemination of study findings into routine clinical practice. We will explore strategies to optimize such dissemination and implementation.

2) Determine the optimal length of FSI intervention.

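### The primary 6MW analysis is a completer ANCOVA that ignores POST1 data from patients lost before POST2; the planned mixed model, fully specified, is the better primary estimate

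*Combined protocol and SAP*

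**What the plan says.** - **Primary model (A1.6, Primary Analysis).** An ANCOVA with "change from baseline at POST2 for the 6MW distance being the response variable". The covariates are group, baseline 6MW, surgical approach and Veteran status. POST1 is not in the model.
- **Decision (A1.6).** "The conclusion about differences between treatment groups will be determined by this single statistical test".
- **Sensitivity analysis (A1.6).** A "mixed-effects model and all available data, with estimation of the change from baseline to POST2 and POST3". Fixed effects, handling of baseline and covariance structure are not given. Then: "If the sensitivity analysis is not consistent with the primary analysis, the results will be considered inconclusive". What counts as consistent is not defined.
- **Missing data (A1.8).** "All participants with outcome measurements will be included in the intent-to-treat analysis". Adjustment methods are set aside because "these methods rely on the untestable assumption that data are" missing at random, and "We will instead focus on preventing missed follow-up visits".
- **Visits (Section IV, A1.3).** 6MW is measured at baseline, POST1, POST2 and POST3. Of POST1 the plan says "The 4-week test will allow for identifying if any changes occur early in the intervention".
- **Numbers.** Section I gives 100 participants. Section IV, A1.1 and A1.7 give 150 (75 per group), and A1.1 expects at least 80 to finish.

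**The concern.** The ANCOVA can use only patients with a POST2 6MW. Loss unrelated to outcome given arm, baseline and strata is sufficient for it to be unbiased. That is as untestable as missing at random, and stronger, because missing at random also allows loss to depend on POST1. So the reason A1.8 gives for avoiding missing-data methods does not favour the completer analysis.

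What is at stake is the reported effect. If, for example, FSI patients who walk poorly at POST1 tend to leave while control losses are unrelated to POST1, the FSI completers look too good. The reverse pattern hides benefit. A 6MW value that could correct for this is already collected in these patients.

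A second problem needs no dropout assumption. A1.6 says that one test settles the conclusion, and then lets another analysis overturn it under an undefined criterion.

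**Working it through.** **1. The plan's own figure.** With 40 per group, SD 81.3 and difference 59.7 (A1.7), the noncentrality is 59.7 / (81.3 × √(2/40)) = 59.7 / 18.18 = 3.284. The noncentral t with 78 df, two-sided 5%, gives power 0.900. The stated 90% reproduces and is not in dispute.

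**2. Loss the plan allows.** 1 − 80/150 = 46.7%; 1 − 80/100 = 20%. Neither is a forecast of loss between randomisation and POST2, so an assumed 10% is added.

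**3. The two estimates.** The completer ANCOVA regresses POST2 on group and baseline in patients with POST2. The likelihood estimate combines two regressions:

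- POST1 on group and baseline in everyone seen at POST1 (group coefficient *a*);
- POST2 on group, baseline and POST1 in those seen at POST2 (group coefficient *b*, POST1 coefficient *c*).

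Effect = *b* + *c* × *a*. When patients who leave do not return, this is the maximum-likelihood estimate from an unstructured model.

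**4. Bias.** Assumed, not in the documents: SD 81.3 m at each visit; baseline correlations 0.6; POST1-POST2 correlation 0.8; early loss random; late loss logistic in POST1 at log-odds 0.5 to 1 per SD. Simulated, absolute bias in metres:

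| Loss before POST2 (before / after POST1) | ANCOVA, one arm depends on POST1 | ANCOVA, arms in opposite directions | Likelihood model |
|---|---|---|---|
| 10% (3 / 7) | 1–2 | 2–5 | under 0.5 |
| 20% (5 / 15) | 3–5 | 5–10 | under 0.5 |
| 47%, mostly early (40 / 7) | 2–4 | 4–8 | under 0.5 |
| 47%, mostly late (15 / 32) | 6–12 | 13–24 | under 0.5 |

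With the same dependence and the same loss rate in both arms, ANCOVA bias is about 0. With the same dependence (log-odds 1) but late loss of 44% in one arm and 20% in the other, it is about 9 m. If 81.3 is the SD of change rather than of distance, the figures in metres rise by about 12% (81.3 / √0.8 = 90.9).

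**5. The consistency rule.** With no true effect and missing-at-random loss:

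- If *consistent* means that both tests are significant, false positives are 2.5–4.3%.
- If the same direction is enough and loss is arm-specific, they are 10.6% at 20% loss (opposite directions, log-odds 1). At the 47% bound they are 6–8% with mostly early loss (log-odds 1) and 7–33% with mostly late loss.

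**6. Precision under random loss.** SE ratio = √((1 − r²) + r² × n₂/n₁), where n₁ and n₂ are the fractions seen at POST1 and POST2, and r = (0.8 − 0.36) / 0.64 = 0.69. At 20% loss this is √(0.527 + 0.473 × 0.80/0.95) = 0.962, a 4% gain. For the two 47% patterns the gain is 3% (early) and 9% (late). Precision is not the main argument.

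**7. Limits of the mixed model.**

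- If loss depends on the unseen POST2 value (47%, mostly late, opposite directions), its bias is 10 and 19 m at log-odds 0.5 and 1. The ANCOVA's is 19 and 35 m.
- If the POST1-POST2 correlation is 0.8 in one arm and 0.5 in the other, a pooled covariance leaves about 2–6 m (one-arm dependence, 20% and 46.7% loss).
- A random-intercept change-from-baseline model still leaves 4–9 m with 47% mostly late loss, so the specification matters.

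**The case against.** **The mixed model and a rule for disagreement are already planned.** This stands in part. If both tests must be significant, the rule controls false positives in every missing-at-random case examined. A reader might infer that the trial as written has inflated type I error; the documents support that only under a loose reading of an undefined word. The rule still leaves the reported estimate uncorrected. It is also protective under the strict reading, so removing it would be a trade-off that the fix does not need.

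**47% is not the dropout at the primary endpoint.** This stands. Section IV, A1.1 enrols before surgery and randomises two weeks after it, subject to physician approval, so some losses may precede randomisation. Completion may also refer to 26 weeks, and loss after POST2 does not touch the primary test. Eighty is the powered sample size, so it reads as a floor. A reader might infer that nearly half the patients will be missing at POST2, or quote biases of 20 m or more; the documents support neither. The POST1-POST2 gap is four weeks of supervised treatment, home or remote testing is allowed, and missed visits are chased.

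**The mechanism is assumed.** This stands too. Visit number and session length are matched, and nothing in the documents shows arm-specific dropout. FSI is the more demanding programme (Table 1 and its notes), which makes differential loss credible but not demonstrated. The sizes follow the assumptions: placing all 46.7% loss after POST1, treating 81.3 as the SD of change and using log-odds 1 gives 15 to 50 m.

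**The mixed model is not immune.** True, as step 7 shows. In that case its bias is roughly half the ANCOVA's, and a delta-adjusted analysis is needed whichever model is primary.

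**Conclusion.** The concern holds in conditional form. The primary analysis leaves out POST1 values that it could use, and the reason given in A1.8 applies at least as strongly to the completer analysis. The ANCOVA estimate is biased if loss depends on POST1 and either the dependence or the loss rate differs by arm. It would be too strong to say that it is biased whenever loss depends on POST1.

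Plausible sizes are about 1–5 m at 10% loss before POST2 and 3–10 m at 20%, against 59.7 m. The outer bound of 47% gives 2–8 m if loss is mostly early and 6–24 m if mostly late. All rest on the assumed correlations and dropout slopes in step 4. The unstructured mixed model avoids this bias provided loss depends only on observed data and the POST1-POST2 relation is similar in both arms.

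Three gaps need no assumption: the mixed model is unspecified, *consistent* is undefined, and nothing probes departures from missing at random. This is a cheap improvement that should be made; it is not a fatal flaw. Confidence is medium because the size is unknown.

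**What to change.** Before unblinding:

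1. Make the POST2 contrast from the planned mixed model the primary estimate. Include all randomised patients with any post-baseline 6MW; use POST1, POST2 and POST3; fit group-by-visit, baseline-by-visit and the stratification factors, with unstructured covariance. First reconcile the strata: A1.6 names Veteran status with surgical approach, A1.7 names sex with surgical approach.
2. Keep the completer ANCOVA as a supporting analysis.
3. Reconcile the two decision sentences in A1.6. If the rule on inconclusive results is kept, define *consistent* numerically. Removing it is optional.
4. Add one delta-adjusted (tipping-point) analysis of unobserved POST2 values.
5. Reword A1.8 so that it does not imply that the completer analysis avoids an untestable assumption.

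If the primary test is not changed, the minimum is to specify the mixed model, define *consistent* and add the delta analysis.

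Cost: SAP wording and slightly more programming, since the visits and a mixed model are already planned. The downside is that the primary estimate then depends on a repeated-measures model.

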Rehabilitation emphasizing *functional strength integration* after THA has the potential to substantially improve postoperative physical function by remediating movement compensations with greater hip abductor strength and recruitment during function, providing greater pelvic control and better movement quality. **Therefore, we propose a randomized controlled trial of 100 participants to determine if an 8-week functional strength integration (FSI) program improves physical function and muscle performance more than control intervention (CON) after unilateral THA.** The secondary goal is to determine if FSI improves movement compensations during functional activity (walking and stair climbing). Outcomes will be assessed pre-operatively (PRE); intervention mid-point, 4 weeks (POST1); intervention end-point, 8 weeks (POST2) (primary endpoint); and late recovery, 26 weeks (POST3).

Aim 1: To determine if FSI results in better *physical function* and *muscle performance* after unilateral THA compared to usual care rehabilitation. Physical function will be measured with standardized performance-based tests [6-Minute Walk (primary outcome), Four-Meter Walk, 30 second sit-to-stand, and Functional Gait Assessment] and self-report measures [Western Ontario and McMaster Universities Osteoarthritis Index (WOMAC) and the Veterans RAND 12-Item Health Survey (VR-12)]. Muscle performance will be assessed with measures of muscle strength (hip abduction force) and muscle endurance (modified Trendelenburg test). Hypothesis 1: The FSI group will have greater physical function and muscle performance improvements than the CON group from baseline to POST2 (primary endpoint), and group differences will persist at POST3.

Aim 2: To determine if FSI intervention more effectively reduces movement compensations than CON intervention after unilateral THA, as measured by *peak internal hip abduction moments* during gait.

Hypothesis 2: The FSI group will have greater increases in surgical-limb peak internal hip abduction moments during gait compared to the CON group from baseline to POST2, and group differences will persist at POST3.

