One hundred-fifty patients aged 50-85 years with hip OA, scheduled for a unilateral, primary THA will be enrolled, with at least 80 patients expected to complete the study. Patients will have a THA performed by surgeons who will refer patients who meet the following criteria: 1) no severe contralateral leg OA (< 5/10 pain with stair climbing) nor other unstable orthopaedic conditions that limit function, 2) no neurological or pulmonary problems that severely limit function, 3) no uncontrolled hypertension or diabetes, and 4) body mass index ≤ 40 kg/m² (for motion capture reliability). Referring surgeons will perform THA using their preferred surgical approach (anterior or posterolateral). Upon referral and prior to surgery (PRE), eligible patients will visit the **GRECC Human Movement Analysis Lab** for informed consent and baseline

measurements. Two weeks after surgery, with physician approval, they will be **randomization into 1 of 2 treatment arms: FSI (experimental) group or CON (control) group**. The randomization process and maintenance of treatment code records will be managed by [name] (biostatistician), who will not be involved in patient testing/treatment. This will maintain the double-blinded condition for participants/researchers collecting data.

A1.2. Rehabilitation

Following THA surgery, standardized **inpatient** rehabilitation programs will be implemented for all patients (Figure 4). Upon returning home, patients in both groups will receive a phone call and/or home visits (if necessary) from a study physical therapist from our research team to ensure safety, provide ADL training, and monitor for complications. Randomization and initiation of study treatment will follow this 2-week recovery period to allow for early recovery before intervention. Following randomization, both groups will participate in an 8-week outpatient rehabilitation program (~40 minutes per session) at the outpatient PT Clinic, or at the

[figure not shown]

Figure 2. Peak internal hip abduction moment changes over time for the pilot-study intervention and control groups for the surgical limb during walking, step-up, and step-down tasks. (n=5 Control; n=10 Intervention)

[figure not shown]

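### The aims plan 100 participants and the methods plan 150; the stated accrual of 2-3 per month does not deliver 150 and reaches 100 only in the upper part of that range

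*Combined protocol and SAP*

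**What the plan says.** Section I (Hypotheses and Specific Aims): "we propose a randomized controlled trial of 100 participants".

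A1.1 Patients sets the enrolment figure: "One hundred-fifty patients aged 50-85 years with hip OA, scheduled for a unilateral, primary THA will be enrolled". The same sentence then gives the number who should finish: "with at least 80 patients expected to complete the study".

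A1.7 Sample Size Estimates: "a 2-sample, 2-sided t-test at the 5% level with 80 patients (40 per group) would have 90% power" for a difference of 59.7 m with an SD of 81.3. It then sets the recruitment target: "We will recruit 150 participants (75/group) to allow for loss to follow-up".

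A1.9 Timeline: "Study enrollment will start in months 3-4 and continue through the first part of year 4, with a targeted accrual rate of 2-3 patients/month". It adds: "Abstract and manuscript preparation will begin in years 2-3, but will increase in year 4". The timeline gives no end month for enrolment and mentions no fifth year.

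No section states a loss percentage. It can only be inferred from the enrolled and completing numbers.

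**The concern.** The plan gives two sample sizes for the same trial, and the accrual projection does not produce the larger one. A reader cannot tell whether the recruitment target is 100 or 150, and so cannot later judge whether enrolment met its target or stopped short.

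The two figures also carry very different allowances for loss around the same 80 patients. If 150 is right, the plan tolerates losing almost half of those enrolled, but the timeline does not supply the patients who make up that margin. If 100 is right, the margin is 20%, and A1.1 and A1.7 overstate it.

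**Working it through.** **1. The plan's power figure (inputs from A1.7).** Two-sample, two-sided t-test, alpha 0.05, n = 40 per group, difference 59.7 m, SD 81.3.

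- Noncentrality = 59.7 / (81.3 × √(2/40)) = 3.284, with 78 degrees of freedom and critical value 1.991.
- Power from the noncentral t = 0.900. The difference detectable at 90% power is 59.67 m.

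The stated 90% reproduces.

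**2. Loss implied by each N (80 from A1.1 and A1.7).**

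- 150 to 80: 1 − 80/150 = 46.7%. Because A1.1 says at least 80, this is an upper limit.
- 100 to 80: 1 − 80/100 = 20.0%.

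**3. Accrual (A1.9).** Yield = months in the window × patients per month, counting months inclusively. Assumption: the first part of year 4 ends somewhere in months 37-42. The shortest window is then month 4 to 37 (34 months) and the longest is month 3 to 42 (40 months). The outer bound runs to the end of year 4: 45 months from month 4, or 46 from month 3.

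| Window | 2/month | 2.5/month | 3/month | Rate needed for 100 | Rate needed for 150 |
|---|---|---|---|---|---|
| 34 months | 68 | 85 | 102 | 100/34 = 2.94 | 150/34 = 4.41 |
| 40 months | 80 | 100 | 120 | 100/40 = 2.50 | 150/40 = 3.75 |
| 45 months (outer bound) | 90 | 112.5 | 135 | 100/45 = 2.22 | 150/45 = 3.33 |
| 46 months (outer bound) | 92 | 115 | 138 | 100/46 = 2.17 | 150/46 = 3.26 |

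At 3 per month, 150 takes 150/3 = 50 months. A start in month 3 or 4 would then end in month 52 or 53, in year 5.

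**4. Loss that the accrual can absorb while leaving 80.**

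- 3/month: 1 − 80/102 = 21.6% to 1 − 80/120 = 33.3%.
- 2.5/month: 1 − 80/85 = 5.9% to 1 − 80/100 = 20.0%.
- 2/month: 80 is not reached in 34 months (68 enrolled), and is reached in 40 months only with no loss. To the end of year 4: 1 − 80/90 = 11.1% to 1 − 80/92 = 13.0%.

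**5. Illustration only: power if the loss were known.** The 34-40 month window enrols 68-120. Power uses the same t-test, before any gain from covariate adjustment.

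| Assumed loss | Evaluable patients | Per group | Power |
|---|---|---|---|
| 20% | 68 × 0.8 = 54 to 120 × 0.8 = 96 | 27 to 48 | 0.754 to 0.945 |
| 46.7% | 68 × 80/150 = 36 to 120 × 80/150 = 64 | 18 to 32 | 0.572 to 0.824 |

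The result depends so heavily on the assumed loss that neither row is a finding about this trial.

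**The case against.** **Two stages of counting.** Consent is taken before surgery, and A1.2 says "Randomization and initiation of study treatment will follow this 2-week recovery period". A plan of 150 consented, 100 randomised and 80 completing would be coherent. It does not survive A1.7, which divides the 150 into 75 per group and attributes the excess to loss to follow-up. That is a count of allocated patients, and no section describes a step from 150 to 100.

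**The timeline is only a projection.** A1.9 gives an anticipated timeline and a targeted rate, not a stopping rule. It alters no test, alpha level or analysis set. This stands, so the fair statement is that the timeline does not deliver 150 at its own target rate, not that 150 could never be recruited.

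**Power.** A reader might infer that the trial is underpowered. The documents do not support that:

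- The calculation for 80 evaluable patients is right.
- The primary endpoint is POST2 at 8 weeks, and A1.8 keeps everyone with outcome measurements in the analysis. A patient lost between weeks 8 and 26 still counts, so 80 patients with POST2 data is an easier target than 80 who finish the study.
- A1.7 expects further precision from covariate adjustment, although it gives no figure.
- At 3 per month, 80 survive losses of about 22-33%.

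**Loss rate.** It could be said that the loss is given implicitly by 150 and at least 80. That yields an upper limit of 46.7%, which is neither stated nor justified as a rate. Its absence, like that of an enrolment end month, would by itself be only missing detail.

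**Conclusion.** The inconsistency is real. Section I plans 100; A1.1 and A1.7 plan 150. The accrual in A1.9 yields 68-120 patients over an assumed 34-40 months, which is 30-82 short of 150. The conclusion about 150 does not rest on the assumed end month: the earliest start, the highest rate and all of year 4 give 138, still 12 short.

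It is tempting to say that the timeline shows 100 to be the intended figure. It does not go that far. In the assumed window 100 needs at least 2.5 per month (40 months) to 2.9 per month (34 months), and 2 per month gives only 68-80.

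The 90% power at 40 per group stands. Whether 80 patients with POST2 data are obtained depends on the accrual rate and on a loss that the plan does not state, so any lower power figure is an illustration. The point should be fixed because the planned sample size is contradicted by the plan's own figures and is cheap to restate.

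**What to change.** Use one N in Section I, A1.1 and A1.7, and make A1.9 agree with it. Two routes would do this.

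1. **Keep 150.** Change Section I to 150 and restate the rate or window so that it yields 150: about 3.75 per month over 40 months, 4.4 per month over 34 months, or 3 per month for 50 months. Cost: a higher recruitment target or a longer timeline.
2. **Keep 2-3 per month and the year-4 end.** Restate N, the loss it allows for, and the expected number evaluable at POST2. Restate power only if that number falls below 80. Cost: a smaller stated N and a smaller margin for loss.

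Under either route, give the assumed loss and the month in which enrolment ends, and say whether N counts patients consented before surgery or randomised two weeks after it. The changes are to wording and planning figures; no visit or assessment is added.
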